Setting: The patients will be recruited from Oncology and Urology clinics at Froedtert Hospital. PCa patients in the clinics who consent to participate in this study will do physical performance testing at each assessment. A trained research assistant (RA) will administer testing and enter data into a secure database. Serious adverse events and study progress for this investigator initiated trial will be monitored by [name] per NCI CCSG guidelines. Recruitment: Based on the number of patients currently seen in these clinics, approximately 2-3 patients will be seen a week who are eligible for this study. A total of 80 patients (40 in each arm) will be enrolled in this pilot study.

[figure not shown]

Table 2: Measures performed over time per group						
	Baseline			3 months		
	SPPB			SPPB		
	HD	MRI	Biopsy	HD	MRI	Biopsy
	falls		. ,	falls		
Control	Χ	X*	X*	Χ	X*	X*
HMB	Χ	X*	X*	Χ	X*	X*

SPPB: Short Physical Performance Battery; HD: hand dynamometer:

* MRI and Biopsy to be done on subset of sample

Data Analysis:

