Study design: The trial will be conducted in two phases, with 40 patients recruited for both phases. After the first 40 patients have been evaluated, a two-sample one-sided t-test comparing the mean lean body mass loss will be conducted. If the one-sided p-value is equal or less than 0.0088, the trial will be stopped for efficacy. If the p-value exceeds 0.3, the trial will be stopped for futility. In all other cases the trial will proceed to the next phase. At the end of the second phase a two-sample one-sided t-test comparing the mean lean body mass loss in the two groups will be conducted at a 5% significance level. Randomization: Randomization will be stratified by exercise status to ensure almost equal representation of both strata in both treatment groups. A block-size of 8 will be used, that is among each 8 consecutive patients exactly 4 will receive each treatment. Due to the presence of strata this blocking will not ensure exactly equal group size, however compared to unblocked randomization it will keep the group-size difference lower. Sample size considerations: The study was powered to detect a smaller lean body mass loss by 0.8 kg in the treated group using a one-sided twosample t-test at a 5% significance level. This effect size corresponds to approximately 50% of the expected lean body mass loss in the control group, and is similar to the effect achieved by an exercise intervention.³⁸ Based on literature review the standard deviation of within-person lean body mass change was assumed to be 1.4kg.^{38,39} The following table shows the power of the study and the probability of early stopping for efficacy/futility with the planned total sample size of 40 subjects per group and one interim analysis after 20 patients. The values are based on 10,000 simulation runs.

Difference in lean body	Probability of early stopping	Probability of early stopping	Overall
mass loss, kg	for efficacy	for futility	power
0	0.9%	70.3%	4.7%
0.4	6.5%	35.4%	33.7%
0.8	26.4%	10%	78.0%
1.2	59.5%	1.5%	97.5%
1.6	86.8%	0.1%	99.8%

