Statistical analysis plan: As described in the study design, the primary outcome of within-person lean body mass change will be analyzed using a one-sided two-sample t-test. This test will be conducted at a 0.88% significance level after 20 patients have been evaluated in both arms, and, if the study proceeds to the end, at a 5% significance level after 40 patients have been evaluated in both arms. The secondary outcomes will be evaluated using a t-test or Wilcoxon rank-sum test as appropriate.

Anticipated Results/Interpretation: We anticipate that body composition will be better preserved in the supplemented group after initiation of ADT. In addition, we expect less functional limitations to mobility in the supplemented group as indicated by greater physical activity as measured by accelerometry. Further we expect physical activity to be positively related to muscle strength and endurance.

Objective 2: Prospectively measure the fatiguability and muscle size using MRI/Phosphorus MRI spectroscopy (³¹P-MRS) in older men with PCa starting on ADT, comparing those who receive HMB + AG versus those who do not.

Rationale: Fatigue is highly prevalent in men with PCa undergoing ADT and can affect QOL. Muscle fatigue could be due decreased oxidative capacity as a primary or secondary effect of the cancer or its treatment. Fatigue could also result from muscle weakness or loss of strength. The later could occur when a smaller amount of muscle has to accomplish the same amount of work as that of a larger amount. 31P- MRS is a non invasive *in vivo* technique which can be used to study phosphorus energy metabolites in conscious humans during exercise. As such, it can help to delineate the causes of muscle fatigue in PCa with ADT. We expect both to play a role. HMB + AG has been shown to increase muscle strength in older patients. It stands to reason that muscle strength and fatiguability would improve in older men with prostate cancer on ADT who receive HMB + AG.

Experimental Design: A subset of consenting patients (estimated 20 per group) will be assessed at time increments as outlined above. Cross sectional area of quadriceps muscle will be assessed using MRI. Muscle fatiguability will be measured as time to task failure (i.e. endurance and PCr recovery) using 31P-MRS at baseline and 3 months.

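### Does the plan place its interim look at conflicting sample sizes: 20 patients, 40 patients, or 20 per arm?

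*Combined protocol and SAP*

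**What the plan says.** All the relevant text is in section 5, under Objective 1.

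- **Recruitment:** "A total of 80 patients (40 in each arm) will be enrolled in this pilot study".
- **Study design:** "The trial will be conducted in two phases, with 40 patients recruited for both phases". The look itself is then defined: "After the first 40 patients have been evaluated, a two-sample one-sided t-test comparing the mean lean body mass loss will be conducted". The stopping limits follow: "If the one-sided p-value is equal or less than 0.0088, the trial will be stopped for efficacy", with a futility stop if the p-value is above 0.3. The final one-sided test is at 5%.
- **Randomization:** stratified by exercise status, in blocks of 8, with the caveat "Due to the presence of strata this blocking will not ensure exactly equal group size".
- **Sample size considerations:** the power table is said to apply "with the planned total sample size of 40 subjects per group and one interim analysis after 20 patients".
- **Statistical analysis plan:** this paragraph refers back to the study design and says "This test will be conducted at a 0.88% significance level after 20 patients have been evaluated in both arms". It gives the final test as 40 evaluated in each arm.

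**The concern.** Three sentences describe the timing of one look in three ways. The sample-size sentence gives a unit for the 40 (per group) but none for the 20, so a literal reader would put the look at 20 patients in total, a quarter of the trial instead of half. The other two descriptions are not strictly the same trigger either. The plan itself concedes that arms may be unequal, so the fortieth evaluated patient need not be the point at which both arms hold 20.

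This would matter if it were a real conflict, because the look can end the trial in either direction and the supplement is compared with no supplement, without a placebo. A look at 10 per arm would raise the chance of a futility stop under the planned 0.8 kg benefit from about 10% to about 23%, and would cost about 10 points of power. A trigger left open between two definitions could also, in principle, be moved.

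**Working it through.** **Inputs (all section 5, Objective 1).** Difference 0.8 kg; SD of change 1.4 kg; efficacy stop at one-sided p ≤ 0.0088; futility stop at p > 0.3; final one-sided test at 0.05; 40 per arm at the end; 80 in total.

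**Step 1: place the look.** Two phases of 40 make 80. At 1:1 allocation, 40 evaluated patients are 40/2 = 20 per arm, at information fraction 40/80 = 1/2. The study design and analysis plan paragraphs therefore describe the same planned look. Only a literal 20 in total (10 per arm, 20/80 = 1/4) would differ.

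**Step 2: interim probabilities at 0.8 kg, from the noncentral t.** SE = 1.4 × √(1/n₁ + 1/n₂); noncentrality = 0.8/SE; df = n₁ + n₂ − 2.

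- 20 per arm: SE = 1.4 × √(2/20) = 0.4427; noncentrality 1.807; df 38. The critical t values are 2.482 (p = 0.0088) and 0.529 (p = 0.3). Efficacy 26.3%, futility 10.0%.
- 10 per arm: SE = 1.4 × √(2/10) = 0.6261; noncentrality 1.278; df 18. The critical t values are 2.613 and 0.534. Efficacy 11.6%, futility 22.7%.

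The plan prints 26.4% and 10%.

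**Step 3: the whole table.** Two-stage simulation, 200,000 trials per row, futility stop binding. Entries are efficacy stop / futility stop / overall power, in %.

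| Difference, kg | Printed | Look at 20 per arm | Look at 10 per arm |
|---|---|---|---|
| 0 | 0.9 / 70.3 / 4.7 | 0.8 / 70.0 / 4.8 | 0.9 / 69.9 / 4.2 |
| 0.4 | 6.5 / 35.4 / 33.7 | 6.6 / 35.3 / 33.4 | 3.8 / 45.5 / 27.8 |
| 0.8 | 26.4 / 10 / 78.0 | 26.5 / 10.0 / 78.5 | 11.6 / 22.8 / 68.1 |
| 1.2 | 59.5 / 1.5 / 97.5 | 59.5 / 1.4 / 97.5 | 27.3 / 8.2 / 91.0 |
| 1.6 | 86.8 / 0.1 / 99.8 | 86.6 / 0.1 / 99.9 | 49.3 / 2.2 / 97.8 |

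The largest gap from the printed values at 20 per arm is 0.5 points (power at 0.8 kg). The plan used 10,000 runs, so the simulation standard error there is √(0.78 × 0.22/10,000) = 0.4 points, and the gap is unremarkable. At 10 per arm every row with a true difference is clearly wrong. In the null row the interim stops cannot separate the readings, because the p-value is then uniform whatever the sample size.

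**Step 4: the efficacy limit.** A two-look O'Brien-Fleming boundary at one-sided 0.05 has a first-look p of 0.0088 at half information and 0.0005 at one quarter. The plan names no boundary, so this is supporting evidence only. The 0.3 futility limit is not tied to any information fraction.

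**Step 5: 40 in total against exactly 20 per arm.** In blocks of 8, an unfinished block can move a stratum at most 2 patients from an even split, so two strata give at most 24:16. Simulated allocations, with the smaller stratum assumed to hold 20%, 30% or 50% of patients (the plan gives no shares), were not 20:20 at patient 40 in about half of trials. At least 90% were within 21:19 and over 99% within 22:18. Both arms reached 20 at a median of 40 to 41 patients, and by 44 at the latest. Interim probabilities at 0.8 kg:

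- 20:20: efficacy 26.3%, futility 10.0%
- 22:18: SE = 1.4 × √(1/22 + 1/18) = 0.4449; efficacy 26.0%, futility 10.2%
- 24:16: SE = 1.4 × √(1/24 + 1/16) = 0.4518; efficacy 25.2%, futility 10.7%

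**The case for a change.** The best case for an edit is that the faulty sentence is the one stating the assumption behind the power table, that the look can end the trial, and that the repair costs two words. A literal reading contradicts the rest of the section, and a binding look in a trial without placebo should have one fixed trigger.

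Part of this stands. The sentence is incomplete, and a tidy revision would add the unit. But the larger futility risk arises only if someone runs the look at 20 in total, against the study design paragraph, the analysis plan and the table that the sentence itself introduces. The point about one trigger is right in principle, but here the candidates lie within 4 patients of each other (40 against at most 44) and change neither interim probability by more than about 1 point. The study design paragraph already fixes a count, 40 evaluated, and the analysis plan refers back to it. Nothing in the text suggests that the look would be timed by the results.

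**Conclusion.** The concern does not hold as a defect in the design. There are not three interim points. There is one, stated consistently in the two operative paragraphs, and a third sentence that omits its unit. An analyst who follows the plan does the look after 40 evaluated patients, about 20 per arm, and obtains the operating characteristics printed, to within 0.5 points in every cell. Inserting the missing unit would change no number, limit, test or conclusion, so this is a clerical slip and no change to the plan is needed.

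This rests on the plan's own assumptions (1:1 allocation, SD 1.4 kg, roughly normal changes, futility stop applied as written) and, for the size of the imbalance, on two exercise strata with assumed shares of 20% to 50% for the smaller one.

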5. STUDY DESIGN AND STATISTICAL CONSIDERATIONS

Objective 1: Prospectively measure the change in body composition, strength, physical performance measures, and falls in older men with PCa starting on ADT, comparing those who receive HMB + AG versus those who do not.

Rationale: Older men with prostate cancer who start on ADT experience clinically significant muscle loss and weakness as a result of treatment, likely contributing to increase risk of falls and fractures and decreased quality of life. Treatments are needed which counteract the loss of muscle mass and strength caused by ADT. HMB + AG, which decreases protein/muscle breakdown, has been shown to increase lean muscle mass and strength in elderly men and women. It seems plausible that HMB + AG could counteract the muscle loss and weakness that men experience as a result of ADT; effectiveness of HMB + AG in men with prostate cancer starting ADT has not been studied.

Experimental Design: We will conduct a prospective cohort pilot study of men age 60 and older with Pca who are about to start ADT. All men will be followed prospectively for 3 months from time of initiation of ADT. Men will be randomized to receive HMB + AG versus no supplement (Figure 2). Assessments will be performed at baseline (before or within 2 weeks of starting ADT) and 3 months (Table 2). Adherence to HMB will be assessed by patient diaries. Functional assessments and basic strength measurements will be performed at baseline and 3 months. These will include the Short Physical Performance Battery (SPPB), a validated measure which evaluates balance, gait, strength, and endurance and has been shown to predictive of morbidity and mortality at 4 years. Hand dynamometer (grip strength, predictive of morbidity and mortality on older patients) and 3 month history of falls will also be assessed. Physical activity will be measured with tri-axial accelerometers (Actigraph, Pensacola FL) that persons will wear on a belt around the waist for 7-days. This has been used previously in men with prostate cancer. Body composition will be measured with Dual-emission X-ray absorptiometry (DXA) scan at baseline and 3 months. Muscle strength will be measured with non-magnetic force transducers and composition will be measured with MRI at baseline and 3 months (SA2). Muscle biopsies will be done on a subset of patients who agree to the procedure (SA3).

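### Randomization is stratified by exercise status but both primary t-tests leave the stratum out; adjusting for it is a small efficiency gain, not the correction of an error

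*Combined protocol and SAP*

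**What the plan says.** All of this is in section 5, Objective 1 of the combined protocol and SAP, mostly under Data Analysis.

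- Randomization: "Randomization will be stratified by exercise status to ensure almost equal representation of both strata in both treatment groups". Blocks of 8 are used, with four patients per arm in each.
- Statistical analysis plan: "the primary outcome of within-person lean body mass change will be analyzed using a one-sided two-sample t-test". It is run at a one-sided 0.88% level after 20 patients per arm and, if the trial continues, at a one-sided 5% level after 40 per arm.
- Study design: "If the p-value exceeds 0.3, the trial will be stopped for futility". The efficacy stop at the same look is at a one-sided p of 0.0088 or less.
- Sample size considerations: the target is a 0.8 kg smaller loss. "This effect size corresponds to approximately 50% of the expected lean body mass loss in the control group", and "the standard deviation of within-person lean body mass change was assumed to be 1.4kg". The table gives 78.0% power at 0.8 kg and 4.7% rejection at no difference. "The values are based on 10,000 simulation runs".
- Secondary outcomes: "The secondary outcomes will be evaluated using a t-test or Wilcoxon rank-sum test as appropriate".

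No stratified or covariate-adjusted analysis appears anywhere, even as a sensitivity analysis. The documents do not define exercise status, give the expected size of its two strata, or say how far lean mass change is expected to differ between them.

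**The concern.** Stratified blocks make the exercise strata nearly equal across arms, so a difference between strata adds little to the true variability of the arm contrast. An unadjusted t-test does not use this. Its pooled variance still contains the spread between strata, so its standard error is too large whenever exercise status predicts the outcome. The test then rejects less often than designed, both under no effect and under a real effect.

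At stake is some power in an 80-patient trial, from a variable already recorded in order to randomize. The same test drives the interim decision, so any conservatism also carries into early stopping. The model has to be chosen before the interim, because picking covariates after seeing outcomes would compromise the test.

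**Working it through.** **Inputs from section 5.** SD of change 1.4 kg; target effect 0.8 kg; 20 per arm at the interim and 40 per arm at the end; stop for efficacy at one-sided p ≤ 0.0088, for futility at p > 0.3; final one-sided 5%; two strata; blocks of 8.

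**Assumptions, because the documents give no figure.** The gap g (difference in mean change between strata) is 0, 0.4 or 0.8 kg. The split runs from 50:50 to 10:90. The 1.4 kg may be the total SD or the SD within strata; the documents do not say which, so both are shown.

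**Step 1: reproduce the plan's table.** Simulating the two-stage t-test (400,000 runs per row, SD 1.4 kg):

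| Difference, kg | 0 | 0.4 | 0.8 | 1.2 | 1.6 |
|---|---|---|---|---|---|
| Plan, overall power | 4.7% | 33.7% | 78.0% | 97.5% | 99.8% |
| Recomputed | 4.9% | 33.2% | 78.5% | 97.5% | 99.9% |

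At 0.8 kg the recomputed early stops are 26.4% (efficacy) and 10.0% (futility), against 26.4% and 10% in the plan. With 10,000 runs, the plan's 78.0% has a simulation SE of √(0.78 × 0.22 / 10,000) = 0.41 points. The table reproduces.

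**Step 2: how much variance the stratum can hold.** With a proportion p in one stratum, the variance between strata is p(1 − p)g².

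- 50:50, g = 0.4: 0.25 × 0.16 = 0.04 kg², which is 2.0% of 1.4² = 1.96.
- 50:50, g = 0.8: 0.25 × 0.64 = 0.16 kg², or 8.2% of 1.96.
- 10:90, g = 0.8: 0.09 × 0.64 = 0.058 kg², or 2.9% of 1.96.

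A rough check of the conservatism at 50:50 and g = 0.8, with 1.4 kg as total SD: if the strata were perfectly balanced, the true SE would be √(1.80/1.96) = 0.958 of the SE that the t-test uses. A single final test with 78 df has a 5% critical value of 1.665. The effective cut-off is then 1.665/0.958 = 1.74, a one-sided rate of about 4.3%.

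**Step 3: the full two-stage design**, with permuted blocks of 8 within stratum, comparing the t-test with a linear model on treatment and stratum at both looks (200,000 runs per scenario). Power at a 0.8 kg effect, 1.4 kg read as within-stratum SD:

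| Split | g = 0: t-test / adjusted | g = 0.4 kg | g = 0.8 kg |
|---|---|---|---|
| 50:50 | 78.6 / 78.6 (0.0) | 78.1 / 78.5 (+0.4) | 76.6 / 78.4 (+1.8) |
| 30:70 | 78.4 / 78.3 (-0.1) | 78.0 / 78.4 (+0.4) | 76.7 / 78.2 (+1.5) |
| 20:80 | 78.5 / 78.5 (0.0) | 78.0 / 78.2 (+0.2) | 77.2 / 78.3 (+1.1) |
| 10:90 | 78.4 / 78.2 (-0.2) | 78.0 / 78.0 (0.0) | 77.6 / 78.2 (+0.5 to +0.6) |

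At 10:90 and 0.4 kg, a separate run gave -0.03 (SE 0.04), so a loss of up to about 0.1 point cannot be excluded. Another run at 20:80 with no gap put the cost at 0.1.

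With 1.4 kg as total SD the gains hardly change, but the level does. At 50:50, power is 78.6% vs 79.1% at 0.4 kg (+0.4) and 79.5% vs 81.2% at 0.8 kg (+1.7). At 20:80 and 0.8 kg it is 79.0% vs 80.1% (+1.1).

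**Step 4: error rate and early stopping at 50:50, g = 0.8.** Overall null rejection is 4.1% to 4.2% for the t-test and 4.7% to 4.8% adjusted, across runs. With total SD 1.4 kg and a true 0.8 kg effect, early futility stopping is 9.2% vs 8.8%.

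**Step 5: do the thresholds carry over?** With no gap, the adjusted test gives overall rejection of 4.8 / 33.2 / 78.2 / 97.4 / 99.9% across the five rows (40,000 runs each), close to the plan's own row. The 0.0088 / 0.3 / 0.05 limits need no change.

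**The case against.** The strongest reply is that nothing is broken. The t-test is valid, errs only on the conservative side, and matches the stated power calculation. The plan gives stratification its own purpose, balance of the strata across arms, and that is met without a model term. For a pilot meant to inform a larger trial, a simple test is defensible. All of this stands.

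It also stands that the benefit rests on assumptions. A 0.8 kg gap is as large as the whole target effect, and about half of the control-arm loss of 0.8/0.5 = 1.6 kg that the plan implies. The sample-size paragraph does compare 0.8 kg with the effect of an exercise intervention, but that is the effect of an assigned programme and says nothing direct about men who differ in exercise status at entry. At a 0.4 kg gap the best-case gain, 0.4 points, is no larger than the simulation error of the plan's own table. With a rare stratum, adjustment can lose a little power: at 10:90 only about 4 of the 40 interim patients fall in the small stratum, fewer than one block.

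A reader might infer three stronger things:

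- **That the type I error is inflated or the design invalid.** The documents do not support this; the departure is downward.
- **That the stated 78.0% is wrong.** It reproduces. Power falls below it only if 1.4 kg is the within-stratum SD and the strata differ materially, and neither is stated.
- **That baseline lean mass should also be a covariate, since "Body composition will be measured with Dual-emission X-ray absorptiometry (DXA) scan at baseline and 3 months".** The change score already uses baseline. The gain depends on a correlation with change that the documents do not give, and if that correlation is weak the extra term loses power.

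What remains against the plan is that the stratum term is nearly free and has not been considered.

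**Conclusion.** The omission is real and its consequence is small. This is an opportunity for efficiency and not an error in the plan. For gaps up to 0.8 kg and splits from 10:90 to 50:50, the stratum term changes power at the target effect by between about -0.2 and +1.8 points. The upper end needs roughly equal strata and a gap as large as the target effect.

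How far the planned t-test is reassuring depends on what the 1.4 kg describes. If it is the total SD, the t-test keeps at least about 78% power in these scenarios. If it is the within-stratum SD, t-test power falls to about 76.6% at a 0.8 kg gap with equal strata, while the adjusted test stays near 78.3%. Adjustment then protects the stated power instead of adding to it.

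The existence of the omission and the direction of its effect are firm. The size is conditional on a gap and a split that only the investigators can judge.

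**What to change.** Before the interim data are seen, amend the statistical analysis plan so that both looks use a linear model of within-person lean mass change on treatment and exercise stratum as recorded at randomization. Test the treatment coefficient one-sided at the existing 0.0088, 0.3 and 0.05 p-value thresholds. Keep the two-sample t-test as a sensitivity analysis. State what exercise status means and name the recorded variable, since the documents do not define it. Say also whether 1.4 kg is a total or a within-stratum SD.

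Confine the change to the primary outcome. It need not be imposed on outcomes analysed by the rank-sum test or on the 10-patient biopsy subset, where a stratum term would cut residual df from 8 to 7. No baseline covariate is proposed.

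The cost is a few sentences and a re-run of the operating-characteristics table, with no new data or patients. The statistical price is one degree of freedom, and at most about 0.2 points of power if exercise status turns out not to be prognostic and one stratum is rare.

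### The primary t-test on lean-mass change is valid on average, but adjusting for the baseline DXA value already collected would protect both looks against chance imbalance at almost no cost

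*Combined protocol and SAP*

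**What the plan says.** All references are to Section 5, Objective 1.

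- **Measurement (Experimental Design):** "Body composition will be measured with Dual-emission X-ray absorptiometry (DXA) scan at baseline and 3 months". Every man with a change score therefore has a baseline value.
- **Interim (Data Analysis, Study design):** after the first 40 men, "a two-sample one-sided t-test comparing the mean lean body mass loss will be conducted". A one-sided p of 0.0088 or below ends the trial for efficacy, and a p above 0.3 ends it for futility.
- **Final (Statistical analysis plan):** "the primary outcome of within-person lean body mass change will be analyzed using a one-sided two-sample t-test", at 5% one-sided. The same paragraph fixes the interim at 20 per arm: "This test will be conducted at a 0.88% significance level after 20 patients have been evaluated in both arms".
- **Covariates:** none is named at either look.
- **Randomization:** stratified by exercise status only, so starting lean mass is left to chance. The planned test does not use the stratum either.
- **Sample size:** "The study was powered to detect a smaller lean body mass loss by 0.8 kg in the treated group", with an SD of change of 1.4 kg. The power table gives 78.0% at 0.8 kg.

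**The concern.** A change score subtracts each man's own baseline. That removes the influence of baseline only if change is unrelated to it. If men with more lean mass lose more kilograms, or if high baseline readings regress towards the mean, part of a chance difference in starting lean mass stays in the comparison of changes.

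The trial gets one randomization, and its interim look has 20 men per arm and can end it for efficacy or futility. If an imbalance then appears, adjusting after the fact is open to challenge, and not adjusting leaves the result in doubt. Naming the covariate beforehand avoids that choice.

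**Working it through.** **1. Inputs.** From the protocol: SD of change 1.4 kg; target 0.8 kg; 20 per arm at the interim and 40 at the end; stop if one-sided p ≤ 0.0088 or p > 0.3; final level 5%. Not in the documents, so assumed: the correlation ρ between baseline lean mass and change, normal data, a linear relation and no dropout.

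**2. Reproducing the plan's table.** Simulating the planned t-test (200,000 trials per row) gives:

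| True difference | Source | Efficacy stop | Futility stop | Overall |
|---|---|---|---|---|
| 0 kg | plan | 0.9% | 70.3% | 4.7% |
| 0 kg | recomputed | 0.88% | 69.9% | 4.8% |
| 0.8 kg | plan | 26.4% | 10% | 78.0% |
| 0.8 kg | recomputed | 26.1% | 10.1% | 78.4% |

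The table reproduces with the interim at 20 per arm.

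**3. What size of ρ is plausible?** Two routes, both resting on assumed spreads of lean mass:

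- *Loss proportional to lean mass.* The plan equates 0.8 kg with about half the control loss, so that loss is 0.8 / 0.5 = 1.6 kg. Then |ρ| = 1.6 × CV / 1.4. An assumed CV of 10-15% gives 0.11-0.17. An assumed mean of 50-60 kg and SD of 5-10 kg (CV 8.3-20%) gives about 0.10-0.23. In an arm losing 0.8 kg the value would be half as large.
- *Equal variances at baseline and 3 months.* |ρ| = 1.4 / (2 × baseline SD). An assumed SD of 5-10 kg gives 0.14-0.07.

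I take 0.1-0.2 as the working range and show 0.3 as an extreme. By the proportional route, 0.3 would need a CV of 0.3 × 1.4 / 1.6 = 26%.

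**4. How much of an imbalance gets through.** A baseline difference of k standard errors shifts the difference in mean change by ρ × 1.4 × k × √(2/n). For k = 1 and n = 20, √(2/20) = 0.316, so the shift is 0.04 kg at ρ = 0.1, 0.09 kg at 0.2 and 0.13 kg at 0.3, against a 0.8 kg target.

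**5. Effect on decisions.** 60,000 two-stage trials per setting, t-test against ANCOVA with baseline as the only covariate. Favourable means the direction that makes the treated arm's loss look smaller. A normal deviate exceeds 1 SE in a given direction with probability 15.9%, about one trial in six. Rates in the first three rows are rounded to whole percents because repeat runs differed by up to about a point.

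| | ρ = 0.1 | 0.15 | 0.2 | 0.3 | ANCOVA |
|---|---|---|---|---|---|
| False positives, favourable imbalance > 1 SE at 40 per arm (t-test) | 6% | 7% | 8% | 10% | about 5% |
| Power at 0.8 kg, unfavourable imbalance > 1 SE at 40 per arm (t-test) | 74% | 72% | 70% | 64% | 77-79% up to ρ = 0.2; 81% at 0.3 |
| Futility stop at 0.8 kg, unfavourable imbalance > 1 SE at 20 per arm (t-test) | 13% | 15% | 16% | 20% | 10-11% |
| Average power at 0.8 kg, all trials (ANCOVA; t-test is about 78.4% throughout) | 78.4% | 78.6% | 79.4% | 81.3% | n/a |

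Opposite tails at ρ = 0.15: false positives fall to about 3.0% with an unfavourable imbalance, and power rises to about 85% with a favourable one.

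At ρ = 0, ANCOVA power is 77.9%. Over all trials, type I error is about 4.7-4.9% for both methods at every ρ.

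**6. Cross-check.** Fixing the interim imbalance at exactly 1 SE, instead of taking all trials beyond it, gives smaller shifts in the same direction. At ρ = 0.1, null rejection is 5.9% with a favourable imbalance, and futility stopping at 0.8 kg is 11.8% with an unfavourable one.

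**The case against.** The strongest reply is that nothing here is wrong. The outcome is already a change score, the test matches the sample-size calculation and the simulated boundaries, and randomization makes it unbiased. All of that stands.

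A reader might infer three stronger claims, which the documents do not support:

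- *That baseline imbalance passes directly into the result.* It does not. Subtraction removes the baseline difference itself, and only the part that works through ρ remains.
- *That the planned error rate or power is misstated.* Both reproduce. The 6-8% and 70-74% figures are conditional on one kind of randomization outcome and are offset by the opposite tail.
- *That the gain in power is substantial.* That would need ρ of 0.3 or more. The documents give no correlation, and their own loss and SD point lower under ordinary assumptions about spread. Up to about 0.15 the average gain is essentially nil.

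Two further limits are fair. Rates conditional on imbalance at 40 per arm include many trials already stopped at 20 per arm, so the interim futility row is the more practical one. And this is a pilot meant to inform a larger trial, which lowers the stakes.

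What the reply does not answer is the single trial in hand. When change depends on baseline, the t-test's error rates vary with the imbalance actually drawn, while those of ANCOVA hardly do.

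**Conclusion.** The point holds as a low-cost improvement, not as a correction of an error. The benefit is protection against the imbalance that happens to occur, at a small interim look that can end the trial. At ρ = 0.1-0.2 the protection is modest: one to three points of false-positive rate, roughly four to eight points of power, and three to six points of wrongful futility stopping, each in about one trial in six. The average power difference is at most about 1 point in that range and about 3 points at 0.3 (81.3 − 78.4 = 2.9).

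All of these sizes depend on the assumed ρ, a linear relation, normal data and complete follow-up. If ρ is near zero, there is essentially nothing to gain.

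**What to change.** In Section 5, Objective 1, amend both the Study design paragraph and the Statistical analysis plan paragraph. At each look, replace the two-sample t-test with a one-sided ANCOVA of lean body mass change on arm, with baseline DXA lean mass as a linear covariate and exercise status, the randomization stratum, as a factor. Keep the p-value limits 0.0088, 0.3 and 0.05; with baseline as the covariate, the simulated overall error stays at about 4.7-4.9%. Report the unadjusted t-test as a sensitivity analysis.

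Cost: no new data or patients. The baseline covariate uses one degree of freedom and the two-level stratum a second. If baseline is unrelated to change, the baseline covariate costs about 0.6 points of power. The effect of adding exercise status was not simulated.
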